Patients that meet the eligibility criteria will undergo PET/CT for baseline imaging and will require tumor tissue for evaluation for PD-L1 expression. Fresh tissue or archival tissue will be obtained and used for PD-L1 analysis. PD-L1 expression will not be required for entry onto the study, given it is unknown if PD-L1 is predictive when pembrolizumab is combined with radiation, and given preclinical data suggesting that radiation leads to an increase in IFN- γ and subsequent PD-L1 expression in the tumor.¹ As highlighted in the study schema, patients will be treated with radiation (1.2Gy BID for total 60Gy) concurrent with pembrolizumab at 200mg intravenous every 3 weeks. The first dosage of pembrolizumab will be given on the first or second day of radiation. After completion of radiation treatment, patients will continue to receive pembrolizumab as a single agent for 3 months. At 3 months after completion of radiation, all patients will undergo a PET/CT to evaluate for response. Patients with a complete response (CR) at 3 months will discontinue pembrolizumab therapy and be observed with clinical exam and repeat CT neck at least every 3 months in the first year and every 6 months in year 2. These patients will then have continued annual follow-up with physical exam and CT neck (as clinically indicated) until the end of the study. Patients with a partial response or stable disease will continue treatment with pembrolizumab up to a total of 24 months (104 weeks) from the first cycle of treatment as long as they do not develop progressive disease, an intolerable toxicity, or other criteria for study withdrawal. These patients will be monitored with CT neck/chest after every 3rd cycle of pembrolizumab or more frequently if clinically indicated. Patients with progressive disease at 3 months post reirradiation will be taken off pembrolizumab and followed for survival. A patient who achieves a CR at 3 months post reirradiation and subsequently progresses may be eligible for retreatment with pembrolizumab as a single agent for up to one year. However, only the time to initial progression will be included in the PFS analysis, the primary endpoint of the study. Determination of response will be as per RECIST 1.1. However, given the experience with immune co-signaling blockade and the possibility of an inflammatory reaction leading to an increase in size of target lesions as well as the development of new lesions initially (before subsequent regression), progressive disease in the absence of clinical deterioration will be verified with repeat CT imaging not less than 4 weeks from prior imaging.^{2,3}

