6. Prior to radiation therapy a dental evaluation will be done if recommended by treating radiation oncologist. Extraction of extensively diseased teeth should be carried out with conservation of restorable teeth where possible. At least 10 days should be allowed for healing of gingivae post-extraction. Because dental evaluation would be required for reirradiation as part of standard of care this evaluation/treatment can begin before consent for the trial.
7. For women of reproductive potential, a urine pregnancy test will be performed within 72 hours prior to first dosage of pembrolizumab. If a urine pregnancy result can't be confirmed as negative, then a serum pregnancy test will be required. Pregnancy testing may be repeated if pregnancy is suspected.
8. CBC to include white blood cells, hgb/hct, platelets and differential. CBC as part of screening for organ function (inclusion criteria # 13) is required to be done within 21 days of start date
9. Tumor imaging will determine the subsequent study treatment plan. Definition of response is detailed in section 7.1.2.6. Subjects with a complete response (CR), partial response (PR), and progressive disease (PD) will require confirmation by repeat CT scan. Subjects will remain on pembrolizumab following section 6.3 until response confirmation. Subjects with confirmed CR will follow Chart 6.2. Subjects with confirmed partial response **or who have** stable disease will **continue** to follow Chart 6.3. Subjects with confirmed progressive disease will follow Chart 6.4. See section 7.1.2.6 for all details on definitions of response.
10. Provide adequate tissue (core or incisional/excisional biopsy) prior to starting study treatment. This tissue will be used for PD-L1 analysis. Fresh tissue or archival tissue sample can only be used. If adequate tissue cannot be safely obtained than the patient may still be able to be enrolled on the trial after discussion with the study principal investigator, as long as FNA was done to confirm recurrent/second primary HNSCC. If the subject signs the Future Biomedical Research (FBR) consent, any leftover tissue that would ordinarily be discarded at the end of the main study will be retained for FBR.
11. Patient Reported Outcome Measures will be completed by the patient. The EORTC QLQ C-30 should be completed first.
12. Coagulation studies will be repeated as clinically necessary.

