7.1.2.6.4 Assessment of Disease

7.1.2.6.4.1 Definitions

Measurable Lesions: Lesions that can be accurately measured in at least one dimension with longest diameter at least ≥ 10 mm on CT scan (or >20 mm by X-ray). Cystic lesions thought to represent cystic metastasis can be considered as measurable lesions.

Malignant Lymph Nodes: To be considered pathologically enlarged and measurable, a lymph node must be ≥ 15 mm when assessed by CT scan.

Non-measurable Lesions: All other lesions < 10 mm or lymph nodes < 15 mm by CT scan.

Target Lesions: All measurable lesions up to a maximum of 2 lesions per organ and up to 5 lesions in total, representative of all involved organs, should be identified as target lesions and recorded and measured at baseline. Target lesions should be selected on the basis of their size (lesions with the longest diameter), be representative of all involved organs, but in addition should be those that lend themselves to reproducible repeated measurements. It may be the case that, on occasion, the largest lesion does not lend itself to reproducible measurement. In this circumstance, the next largest lesion which can be measured reproducibly should be selected. A sum of the diameters (longest for non-nodal lesions, short axis for nodal lesions) for all target lesions will be calculated and reported as the baseline sum diameters. If lymph nodes are to be included in the sum, then only the short axis is added into the sum. The baseline sum diameters will be used as reference to further characterize any objective tumor regression in the measurable dimension of the disease.

Non-target Lesions: All other lesions (or sites of disease) including any measurable lesions over and above the 5 target lesions should be identified as non-target lesions and should also be recorded at baseline. Measurements of these lesions are not required, but the presence, absence, or in rare cases unequivocal progression of each should be noted throughout follow-up.

7.1.2.6.4.2 Evaluation of Disease Response

Response determination will be defined based on RECIST 1.1. (Table 8).

Table 8. Definition of Response in Target Lesions.

Response	Definition
Complete Response (CR)	Disappearance of all target lesions*
Partial Response (PR)	At least a 30% decrease in the sum of the diameters of target lesions, taking as reference the baseline sum diameters

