Progressive Disease (PD)	At least a 20% increase in the sum of the diameters of target lesions compared to baseline sum of target lesions, or any new lesions
Stable Disease (SD)	Neither sufficient decrease to qualify as a PR or sufficient increase to qualify as PD

*After treatment of SCCHN patients with radiation it may be difficult to distinguish residual disease from treatment effect/normal tissue. This will be a critical consideration at 3 months post completion of radiation. As detailed above PET/CT can play a significant role in determination of residual disease at 3 months post completion of radiation. If a target lesion has decreased in size but has not completely resolved and the lesion is not PET avid (defined as an SUV that is not higher than background soft tissue) then the patient is considered to have a complete response. If a target lesion has decreased in size, but has not completely resolved, and it has any PET activity a biopsy can be done at the discretion of the investigator. If a biopsy done and is negative then the patient will be considered to have a complete response. If the biopsy shows residual malignancy or a biopsy is not done then the patient will be considered to have a partial response or stable disease as determined by RECIST 1.1.

Per RECIST 1.1, response should be confirmed by a repeat CT scan. The scan for confirmation of response may be performed at the earliest 4 weeks after imaging that showed response (if clinically indicated) or at the next scheduled scan.

Lesions that can be measured clinically on physical exam (skin lesions or palpable lymph nodes) will be measured by the investigator with the longest axis recorded. These measurements can be used to guide clinical decision making, for example prompting an earlier CT scan to evaluate disease. However, only measurements based on radiology will be used to determine response.

Table 9. Assessment of Non-Target Lesions

Response	Definition
Complete Response (CR)	Disappearance of all non-target lesions
Incomplete Response/Stable Disease (SD)	Persistence of one or more non-target lesions
Progressive Disease	Appearance of one or more new lesions and/or unequivocal progression of existing non-target lesions

Although a clear progression of “non-target” lesions only is exceptional, in such circumstances, the opinion of the treating physician should prevail.

7.1.2.6.4.3 Evaluation of Best Overall Response

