8.2.3 Efficacy

Endpoints Primary

Progression-free survival (PFS) – Progression free survival is defined as the time from the initiation of treatment to the first documented disease progression per RECIST 1.1 or death due to any cause, whichever occurs first. If a patient recurs and is eligible for retreatment, then only the time to the initial recurrence will be included in the evaluation of PFS. Patients who are alive with no evidence of disease at the time of last contact will be censored at that date.

Secondary

Overall Response Rate (ORR) – The overall response rate is defined as the percentage of the patients who have a complete response (CR) or partial response (PR) as defined by RECIST 1.1. The patient's best overall response rate defined as the best response recorded from the start of the treatment until disease progression will be recorded.

Clinical Benefit Rate (CBR) - Clinical benefit rate is the percentage of patients that have achieved a complete response, partial response, and stable disease as defined by RECIST 1.1.

Time to in-field progression – The time to in-field progression is defined as the time from initiation of treatment to progression of disease within the radiation field.

Overall Survival – Overall survival is defined as the time from first treatment until death. Patients who are alive will be censored at the last date of patient contact.

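### Sections 2.1 and 7.1.4.1 stop pembrolizumab at a complete response, Section 6.1 continues it until a repeat CT confirms, and nothing says what that CT must show when the response rests on PET or biopsy

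*Combined protocol and SAP*

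**What the plan says.** **Treatment at a CR.** Section 2.1: "Patients with a complete response (CR) at 3 months will discontinue pembrolizumab therapy and be observed with clinical exam". Section 7.1.4.1 likewise has subjects stop once they attain a CR. Neither mentions confirmation. Section 6.1 footnote 9 requires CR, PR and PD at the week-17 imaging visit to be confirmed by a repeat CT, and adds: "Subjects will remain on pembrolizumab following section 6.3 until response confirmation". Only a confirmed CR then moves to chart 6.2. Section 7.1.5.2.1 makes a confirmed CR one of the routes to retreatment, whereas Section 2.1 holds out possible retreatment after any 3-month CR that later progresses.

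**What a CR is.** Table 8 (Section 7.1.2.6.4.2) gives "Disappearance of all target lesions". Its footnote adds two routes for a lesion that is still visible. The first reads "If a target lesion has decreased in size but has not completely resolved and the lesion is not PET avid"; such a patient is a CR, with no minimum shrinkage. The second covers a lesion with PET activity: "If a biopsy done and is negative then the patient will be considered to have a complete response". That biopsy is at the investigator's discretion. PR requires "At least a 30% decrease in the sum of the diameters of target lesions", and a smaller decrease is SD.

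**Confirmation.** The same section asks for a repeat CT, at the earliest 4 weeks later if clinically indicated, or at the next scheduled scan. Section 7.1.2.6.3 makes later imaging CT of the neck, or MRI, and schedules no further PET.

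**The endpoint.** Section 8.2.3 counts patients with "complete response (CR) or partial response (PR) as defined by RECIST 1.1" and takes the best response recorded before progression. It refers neither to the PET/biopsy rule nor to confirmation.

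**The concern.** A site holding a week-17 PET/CT that shows a CR has two instructions that cannot both be followed: stop, or stay on chart 6.3 until the repeat CT. If the CR was called on PET or biopsy, the repeat CT may still show the lesion, and the site has no criterion for deciding whether that confirms the response.

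Three things depend on how a site resolves this:

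- **Exposure and follow-up chart.** The path sets the doses given while confirmation is pending. It also sets the scan interval: every 3 months in the first year on chart 6.2, after every third cycle (about 9 weeks) on chart 6.3.
- **Retreatment.** A patient stopped under Section 2.1 without a confirming scan may fail the confirmed-CR condition in Section 7.1.5.2.1.
- **Meaning of the response rates.** A reader of Section 8.2.3 would expect ORR to follow the size criteria of Table 8. The footnote lets a patient with less than 30% shrinkage count as a responder.

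**Working it through.** The plan states no figure for this point, so there is none to reproduce. The check compares the sections and counts doses and patients.

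**1. Doses while confirmation is pending.** Inputs: 21-day cycles; imaging at week 17 (Section 6.1); confirmation CT at 4 weeks or at the next scheduled scan (Section 7.1.2.6.4.2); CT after every third cycle on chart 6.3 (footnote 5), counted here from cycle 7. Cycle k starts in week 3k − 2.

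- Cycle 6: 3 × 6 − 2 = week 16. Cycle 7: week 19. Cycle 8: week 22. Cycle 9: week 25. Cycle 10: week 28.
- Sections 2.1 and 7.1.4.1 read literally: 0 doses after the week-17 scan.
- Section 6.1 footnote 9, CT at week 17 + 4 = 21: cycle 7 only, so 1 dose.
- Section 6.1 footnote 9, next scheduled CT before cycle 10: cycles 7, 8 and 9, so 3 doses.

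The visit window is ±7 days. A scan in week 18 puts the earliest CT in week 22, where cycle 8 also falls, so the first case could become 2 doses.

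**2. Classification of a residual lesion.** Illustration: one target lesion of 40 mm at baseline, not PET avid at week 17.

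| Week-17 size | Decrease | Footnote to Table 8 | Table 8 by size |
|---|---|---|---|
| 36 mm | 4/40 = 10% | CR | SD |
| 30 mm | 10/40 = 25% | CR | SD |
| 28 mm | 12/40 = 30% | CR | PR |
| 20 mm | 20/40 = 50% | CR | PR |
| 0 mm | 100% | CR by disappearance | CR |

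CR status differs in every row with a residual lesion. Responder status differs only in the first two rows. Even there ORR changes only if no other scan gives a response by size.

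**3. Size of the shift.** N = 48 (Section 8.2.2), so each reclassified patient moves a rate by 1/48 = 2.1 percentage points. The documents give no frequency for residual-lesion CRs. As an assumption only, take 5 to 20 of the 48:

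- CR rate: 5/48 = 10.4 points to 20/48 = 41.7 points.
- ORR, if none of them shrank by less than 30%: 0.
- ORR, if 25% did: 1.25/48 = 2.6 to 5/48 = 10.4 points.
- ORR, if 50% did: 2.5/48 = 5.2 to 10/48 = 20.8 points.

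**4. Other endpoints.** Clinical benefit rate counts CR, PR and SD alike, so it does not move. PFS runs from start of treatment to first progression or death, and neither event is defined by CR status. The path can change when progression is looked for, but not what counts as progression.

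**The case against.** The best defence is that the plan can be read coherently. Section 2.1 is an overview, Section 6.1 footnote 9 is the operational rule, and Section 7.1.5.2.1 also speaks of a confirmed CR, so confirmation may be implied throughout. The PET/biopsy rule stands openly in the footnote to the CR row of Table 8 and is therefore part of this trial's definition. That footnote explains that residual tissue after radiation may be treatment effect. On that view, a repeat CT with no regrowth and no new lesion confirms the CR. ORR is a secondary endpoint with no threshold, test or planned historical comparison.

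Much of this stands, and it rules out several stronger readings.

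- A reader might infer that CT cannot confirm a PET-defined CR. The documents do not support that: no section says the repeat CT must be re-read by size alone, and absence of regrowth could serve. What is missing is the statement of a criterion.
- A reader might set 6 cycles against about 35 (104 weeks / 3 = 34.7). That is not the size of the stop/continue conflict. It needs the CT to be re-read as PR or SD, and then a patient who stays on drug for the full 24 months. Chart 6.3 footnote 1 also moves anyone who develops a CR in that phase to chart 6.2.
- A reader might put the ORR shift at 10 to 21 points. That assumes a frequency the documents do not give, and the shift may be zero. Under the best-recorded-response wording, a CR recorded at week 17 is also not clearly erased by a later reading.
- A reader might conclude that the ORR cannot be compared with published RECIST 1.1 rates. RECIST 1.1 is adopted by citation and its text is not supplied, so this cannot be settled here.

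Two things survive the defence. Section 7.1.4.1 is a procedural section, not an overview, and it omits confirmation too. And no-regrowth is a sensible reading that the protocol nowhere states.

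**Conclusion.** The point holds as a contradiction in the current text together with a missing definition. Sections 2.1 and 7.1.4.1 on one side, and Section 6.1 footnote 9 on the other, give different instructions for the same patient. The literal difference is 1 dose with a week-21 CT or 3 doses with the next scheduled CT, against none, assuming 3-week cycles on schedule. A longer difference arises only if the repeat CT is re-read by size as PR or SD.

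The CR rate depends on which rule is applied for every CR with a residual lesion. ORR depends on it only where shrinkage is under 30%, at 2.1 points per patient; how many such patients there will be is unknown and may be none. Clinical benefit rate and the definition of PFS are unaffected. The textual conflict does not rest on any assumed frequency. No view is taken on which treatment rule is right.

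**What to change.** - **Treatment path.** Reconcile Sections 2.1, 6.1 footnote 9, 7.1.2.6.4.2, 7.1.4.1 and 7.1.5.2.1 so that a single path applies while confirmation of a CR is pending and the retreatment condition matches it. Which path is for the investigators and sponsor to decide.
- **Confirmation criterion.** In Section 7.1.2.6.4.2, state what the repeat CT must show to confirm a CR that was called on PET or biopsy with a lesion still visible.
- **Endpoint.** In Section 8.2.3, state whether ORR is confirmed or unconfirmed. Report ORR and CR rate twice: by the RECIST 1.1 size criteria of Table 8 alone, and with the PET/biopsy modification, labelled as such.

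The cost is a protocol clarification and one extra response table built from measurements already planned. No new scans are needed.

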5.9 Subject Withdrawal, Replacement and Criteria for Early Trial Termination

5.9.1 Subject Withdrawal/Discontinuation Criteria

Subjects may withdraw consent at any time for any reason or be dropped from the trial at the discretion of the investigator should any untoward effect occur. In addition, a subject may be withdrawn by the Investigator if enrollment into the trial is inappropriate, the trial plan is violated, or for administrative and/or other safety reasons. Specific details regarding discontinuation or withdrawal are provided in Section 7.1.4 – Other Procedures.

A subject must be discontinued from the trial treatment for any of the following reasons:

- The subject withdraws consent.
- Confirmed radiographic disease progression. See Section 7.1.2.6
- Unacceptable adverse events as described in Section 5.4.2
- Intercurrent illness that prevents further administration of treatment
- Investigator's decision to withdraw the subject
- The subject has a confirmed positive serum pregnancy test
- Noncompliance with trial treatment or procedure requirements
- The subject is lost to follow-up

- Completed 24 months of treatment with pembrolizumab
 - Note: 24 months (104 weeks) of study medication is calculated from the date of first dose. Subjects who stop pembrolizumab after 24 months may be eligible for up to 12 months of additional study treatment if they progress after stopping study treatment provided they meet the requirements detailed in Section 7.1.5.2.1.
- Administrative reasons

The End of Treatment and Follow-up visit procedures are listed in Section 6 (Protocol Flow Chart) and Section 7.1.5 (Visit Requirements). After the end of treatment, each subject will be followed for 30 days for adverse event monitoring (serious adverse events will be collected for 90 days after the end of treatment as described in Section 7.2.3.1). Subjects who discontinue for reasons other than progressive disease will have post-treatment follow-up for disease status until disease progression, initiating a non-study cancer treatment, withdrawing consent or becoming lost to follow-up. After documented disease progression, each subject will be followed by telephone for overall survival until death, withdrawal of consent, or the end of the study, whichever occurs first.

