13. A repeat biopsy may be needed to confirm disease status. See section 7.1.2.6.4 Assessment of Disease
14. Comprehensive serum chemistry panel is done as part of screening for organ function (inclusion criteria #13) is required within 21 days of start date
15. Starting with cycle 2 of pembrolizumab, CBC and CMP required prior to giving dosage can be done within 48 hours of dosage.
16. If Hep C Ab is positive a Hep C virus RNA PCR can be checked. If the Hep C virus RNA PCR is negative then the patient does not have active Hep C and therefore would still qualify for the trial.

6.2 Follow Up Phase for Patients Who Achieve a CR at Any Point During the Study or Who Complete Up to 24 Months of Pembrolizumab Without Progression of Disease.¹

Trial Period: Follow Up	Visits during the first year after the last dosage of pembrolizumab ²						Annually after 24 M visit
	3M	6M	9M	12M	18M	24M	
Visit Window	+/- 2Wk	+/- 2Wk	+/- 2Wk	+/- 2Wk	+/- 2Wk	+/- 2Wk	+/- 2 weeks
Clinical Procedures/Assessments							
Concomitant Medication Review	X	X	X	X	X	X	X
Adverse Events	X	X	X	X	X	X	X
ECOG Performance Status	X	X	X	X	X	X	X
Directed Physical Examination	X	X	X	X	X	X	X
Vital Signs and Weight ⁷	X	X	X	X	X	X	X
Efficacy Measurement							
Tumor Imaging ^{4,5}	X	X	X	X	X	X	X ⁸
Laboratory Procedures/Assessments							
Comprehensive Serum Chemistry Panel	X	X	X	X	X	X	X
CBC with Differential	X	X	X	X	X	X	X
T3, FT4 and TSH				X		X	X
Patient Reported Outcomes⁶							
EORTC QLQ C-30	X	X	X	X	X	X	X
EORTC QLQ-H&N35	X	x	X	X	X	X	X

1. Patients will undergo follow up as per this table until progression, withdrawal of consent, initiation of non-protocol anti-cancer treatment(s) or death, whichever occurs first. Definition of "first year" and "second year" are from the time of last pembrolizumab dosage. Patients who recur or progress may be eligible for retreatment discussed in section 7.1.5.2.1.

2. During the first year of follow up patients will be seen at least every 3 months. The patient can be seen more frequently if clinically indicated.

3. During the second year of follow up patients will be seen at least every 6 months. The patient can be seen more frequently if clinically indicated.

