Concomitant Medication Review	X	X	X	X	X	X	X	X	X		
Laboratory Procedures/Assessments											
CBC with Differential	X	X	X	X	X	X	X	X	X		
Comprehensive Serum Chemistry Panel	X	X	X	X	X	X	X	X	X		
Urinalysis ⁵				X			X			X ³	
T3, FT4, TSH ³				X			X			X ³	
Patient reported outcomes											
EORTC QLQ C-30	X		X		X		X		X	X ⁴	
EORTC QLQ-H&N35	X		X		X		X		X	X ⁴	
Efficacy Measurements											
Tumor Imaging ⁵			X ⁵		X ⁵		X ⁵		X ⁵	X ⁵	

1. Patients that develop a complete response during this phase of treatment will be followed as per table 6.2.
2. Patients will continue treatment with pembrolizumab for up to 24 months (from first dosage) or until progression of disease, complete response, discontinuation because of toxicity, or withdrawal from study.
3. Urinalysis and T3, FT4, TSH to be drawn before every 4th cycle (i.e. Cycle 18, Cycle 22, etc.).
4. EORTC QLQ C-30 and EORTC QLQ-H&N35 will be filled out by the patient every other cycle. The EORTC QLQ C-30 should be completed first.
5. Tumor imaging with CT neck and chest with IV contrast will be obtained after each 3rd cycle (or sooner if clinically indicated) Imaging should be reviewed to determine disease status prior to giving every 4th cycle . Definition of response is as per section 7.1.2.6.4. If the investigator feels that MRI will be the best way to follow the patient's head and neck disease subsequently, then an MRI of the neck should be done at baseline as well. However, CT scan is encouraged over MRI.
6. Vital signs to include temperature, pulse, respiratory rate, blood pressure, and oxygen saturation as measured by pulse oximeter.

6.4 Follow Up Phase for Patients with Progressive Disease or Who Discontinue Treatment Because of Toxicity or Any Other Reason (other than completing all eligible cycles of pembrolizumab treatment).

These patients will be taken off of pembrolizumab and enter the follow up phase.

Trial Phase	Safety Follow-up	Follow-up		Survival Follow-up ¹
Time from Last pembrolizumab Dose	30 days	3 months	6 months	Starting at 9 months
Visit	Safety Follow up visit	Follow up visit 1	Follow up visit 2	NA
Scheduling Window	+/- 3 days	+/- 7 days	+/- 7 days	+/- 7 days
Administrative Procedures				
Review Medications	X	X	X	
Subsequent Antineoplastic Therapy	X	X	X	X
Survival Status				X
Clinical Procedures/Assessments				
Review Adverse Events	X	X	X	
ECOG Performance Status	X	X	X	
Directed Physical Exam	X	X	X	
Vital Signs and Weight ³	X	X	X	
Laboratory Procedures/Assessments				

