CBC with Differential	X	X	X	
Comprehensive Serum Chemistry Panel	X	X	X	
Patient Reported Outcomes²				
EORTC QLQ C-30	X	X	X	
EORTC QLQ-H&N35	X	X	X	

1. During survival follow-up patients should be contacted by telephone every 12 weeks to assess for survival status until death, withdrawal of consent, or the end of the study, whichever occurs first.
2. The EORTC QLQ C-30 should be completed first.
3. Vital signs to include temperature, pulse, respiratory rate, blood pressure, and oxygen saturation as measured by pulse oximeter.

4.

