7.1.5.4 Follow-up Visits

Subjects who discontinue trial treatment for a reason other than disease progression or withdrawal of consent will move into the Follow-Up Phase and should be assessed as per Section 6.2. Every effort should be made to collect information regarding disease status until the start of new anti-neoplastic therapy, disease progression, death, end of the study or if the subject begins retreatment with pembrolizumab as detailed in Section 7.1.5.2.1. Information regarding post-study anti-neoplastic treatment will be collected if new treatment is initiated. If a new anti-neoplastic treatment is initiated during this phase, the patient will then be followed as per Section 6.4.

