7.1.5.4.1 Survival Follow-up

Once a subject experiences confirmed disease progression or starts a new anti-cancer therapy, the subject will be followed per Section 6.4. Starting at 9 months from the last pembrolizumab dose, the patient will move into the survival follow-up phase. In this phase, patients should be contacted by telephone every 12 weeks to assess for survival status until death, withdrawal of consent, or the end of the study, whichever occurs first.

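### Chart 6.4's title conflicts with Sections 5.9.1 and 7.1.5.4 on patients who stop pembrolizumab without progression, so their tumor imaging for the primary endpoint is unclear

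*Combined protocol and SAP*

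**What the plan says.** The patient in question stops pembrolizumab without progression, without a complete response and before 24 months, for example because of toxicity.

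- **Chart 6.4, title:** "Follow Up Phase for Patients with Progressive Disease or Who Discontinue Treatment Because of Toxicity or Any Other Reason". The one exception is completing all eligible cycles. The chart has visits at 30 days, 3 months and 6 months, with examination, laboratory and quality-of-life rows but no imaging row. From month 9, note 1 applies: "During survival follow-up patients should be contacted by telephone every 12 weeks to assess for survival status until death".
- **Chart 6.2, title:** "Follow Up Phase for Patients Who Achieve a CR at Any Point During the Study or Who Complete Up to 24 Months". The rest of the title limits the 24-month group to those whose disease has not progressed. Its notes 4 and 5 schedule neck CT every 3 months in year 1 and every 6 months in year 2.
- **Section 7.1.5.4:** patients who stop for "a reason other than disease progression or withdrawal of consent will move into the Follow-Up Phase and should be assessed as per Section 6.2". They change chart later: "If a new anti-neoplastic treatment is initiated during this phase, the patient will then be followed as per Section 6.4".
- **Section 5.9.1:** "Subjects who discontinue for reasons other than progressive disease will have post-treatment follow-up for disease status until disease progression", or until certain other end points such as non-study cancer treatment.
- **Section 7.1.5.4.1:** "Once a subject experiences confirmed disease progression or starts a new anti-cancer therapy, the subject will be followed per Section 6.4".
- **Chart 6.1, note 9:** "Subjects with confirmed progressive disease will follow Chart 6.4".

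Section 8.2.3 defines PFS by the first documented RECIST 1.1 progression or death. Section 8.2.2 includes all patients and tests the result in a single arm against a fixed median of 8 months.

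**The concern.** One foreseeable group of patients is given two follow-up schedules, one with tumor imaging and one without. The supportive-care sections provide for permanent discontinuation for several toxicities. Section 5.10 does not allow a patient who withdraws for toxicity to be replaced, so these patients stay in the PFS analysis.

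Under the response rules in Section 7.1.2.6.4.2, only radiological measurements determine response. The directed examination in Chart 6.4 can prompt a scan but cannot itself supply a RECIST measurement. If a site follows the Chart 6.4 title, a progression after the 3-month PET/CT may be found late or only through death. There is no control arm in which the same loss would occur, so late detection would shift PFS in one direction relative to the 8-month benchmark. A progression that was not imaged at the time cannot be dated reliably afterwards.

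**Working it through.** **1. The passages side by side**

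| Source | Where it sends this patient | Scheduled tumor imaging |
|---|---|---|
| Chart 6.4 title | Chart 6.4 | None |
| Chart 6.2 title | Not clearly named | Neck CT, years 1 and 2 |
| Section 7.1.5.4 | Chart 6.2; Chart 6.4 only after new treatment | As Chart 6.2 |
| Section 5.9.1 | No chart named | Disease status until progression |
| Section 7.1.5.4.1; Chart 6.1 note 9 | By implication not Chart 6.4, which is described for progression or (7.1.5.4.1) new therapy | – |

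The Chart 6.2 title could be read loosely, so that stopping early counts as completing up to 24 months. The patient then fits both titles and the conflict remains. Section 7.1 calls the charts a summary, which favors the body text. Section 5.9.1, however, refers to both Section 6 and Section 7.1.5 for follow-up procedures and does not rank them.

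**2. The plan's own power figure**

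Inputs from Section 8.2.2: N = 48, accrual over 24 months (2 per month), 12 months of maturation, medians of 8 and 12 months, one-sided 5%. Exponential PFS is assumed.

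- Under the alternative, λ1 = ln 2/12 = 0.0578. Event probability = 1 − (e^(−12λ1) − e^(−36λ1))/(24λ1) = 1 − (0.500 − 0.125)/1.386 = 0.7295. Expected events = 48 × 0.7295 = 35.0.
- Power = Φ(ln 1.5 × √35.0 − 1.645) = Φ(0.754) = 77.5%. The plan states 78%, so it reproduces.

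**3. How many patients could be affected**

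The documents give no discontinuation rate. I assume that 10% (4.8) or 20% (9.6) of 48 are liable to leave imaging at a time uniform between 1.2 months and h. Under the null, λ0 = ln 2/8 = 0.0866.

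- h = 6: mean probability of still being progression-free = (0.901 − 0.595)/(0.0866 × 4.8) = 0.737. Affected: 4.8 × 0.737 = 3.5, or 9.6 × 0.737 = 7.1.
- h = 24: (0.901 − 0.125)/(0.0866 × 22.8) = 0.393. This gives 1.9 or 3.8, and about 1.8 or 3.5 once patients whose data cut-off comes first are removed.

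**4. Effect if patients are carried as progression-free to death or last contact**

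This is a simulation of 100,000–200,000 trials per setting. The statistic is √D × ln(Sλ0/D), with D events and S total follow-up, rejecting above 1.645. Ranges cover two assumption pairs: 70% of PFS events are progressions with a median of 3 months from progression to death, or 85% with 4 months. With full imaging there are 40.9 null events, error is 4.05% and power is 78.5%.

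One-sided error when every liable patient is misrouted and no later progression is detected:

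| Leaving window (months) | 10% liable | 20% liable |
|---|---|---|
| 1.2–6 | 5.5–6.6% | 7.3–9.9% |
| 1.2–12 | 5.2–6.0% | 6.6–8.3% |
| 1.2–24 | 4.7–5.1% | 5.5–6.4% |

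A repeat run gave 4.8–6.8% and 5.4–9.8% from a baseline of 4.2%. Milder settings:

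- Keeping the 3-month PET/CT (taken as month 4), h = 6: 5.4–6.4% and 7.1–9.4%.
- Half of later progressions detected: 4.7–5.2% and 5.5–6.5% for h = 6; 4.4–4.6% and 4.7–5.1% for h = 24.
- 10% liable with half of them routed per Section 7.1.5.4: about 4.4–5.1%.

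**5. Effect if patients are censored on leaving**

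Error stays at 4.0–4.1%. For h = 6, power is 75.7% (10%) or 72.3% (20%), a fall of 2.8 or 6.2 points from 78.5%. For h = 24 it is 77.2% or 75.9%, a fall of 1.3 or 2.6 points. A repeat run gave falls of up to about 7 points at 20%. Leaving is independent of prognosis here, so informative censoring is not modeled.

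**The case against.** The strongest reply is that one chart title is out of line with text that otherwise agrees. Sections 5.9.1, 7.1.5.4 and 7.1.5.4.1 and note 9 of Chart 6.1 all point the same way, and Section 7.1 describes the charts as a summary. Section 7.1.5.4 also asks sites to make every effort to collect disease status for exactly this group. A site would have to overlook two explicit instructions for disease status to go uncollected.

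Other safeguards remain:

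- Deaths still count as events.
- Section 2.1 requires the 3-month PET/CT of all patients.
- Chart 6.4 keeps examinations to month 6 and records later antineoplastic therapy.
- Section 7.1 allows unscheduled procedures.

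All of this stands. It rules out the reading that the plan withholds imaging from these patients: the body text requires it, and the fault lies in the chart titles.

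A reader might also infer that Section 8.2.3 turns each telephone call into progression-free time. Its censoring sentence covers patients alive with no evidence of disease. A patient with a partial response or stable disease has residual disease, so the sentence does not literally cover that patient. Carrying such patients forward is one possible reading, not the plain one.

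The safeguards do not supply scheduled imaging after the 3-month scan, and they do not tell a site which chart prevails.

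**Conclusion.** The inconsistency is real and explicit. It should be corrected, but it does not show that the primary analysis is invalid. A site working from chart titles could miss or delay progressions that count in PFS.

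The documents do not support treating an inflated type I error as established. A rise from about 4% to about 5–7% (10% liable) or 5–10% (20% liable) needs four conditions together: the assumed share, every liable patient misrouted despite Sections 5.9.1 and 7.1.5.4, no later progression detected, and the carry-forward reading. With half routed correctly, the error at 10% is about nominal. Under non-informative censoring on leaving, the cost is power: about 1–3 points at 10% and, allowing for simulation error, about 2–7 points at 20%.

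The figures show direction and order of size only. They also rest on exponential PFS and on a test statistic that Section 8.2.2 does not name. The finding rests on the conflicting passages and would stand without the figures.

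**What to change.** Reconcile the titles of Charts 6.2 and 6.4 with Sections 5.9.1, 7.1.5.4 and 7.1.5.4.1, so that the documents give one disease-assessment schedule for patients who stop without progression. Section 7.1.5.4 already calls for the Chart 6.2 tumor imaging until progression or new anti-cancer therapy, with Chart 6.4 afterwards, so aligning the titles to it adds no scan. The sponsor should confirm the choice.

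Keep the 30-day safety visit required by Section 7.1.5.3.1. Chart 6.2 has no column for it, whereas Chart 6.4 does, so it could be lost when the titles are changed.

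The cost is an edit to two chart titles in an amendment and notice to the sites.
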